4.10 Handling of Missing Data

Handling of missing data, if applicable, is discussed in the relevant sub-sections of Section 5.

5 STATISTICAL ANALYSIS: DEFINITIONS, DERIVATIONS, CALCULATIONS AND METHODOLOGY

5.1 Patient Disposition

5.1.1 Disposition and Withdrawals

The following disposition data will be collected:

- date of informed consent
- re-screening status
- date of study termination
- study completion status
- the primary reason for premature study termination

Screening failures will be all patients who discontinued before blood donation .

A patient may have multiple enrolments if they discontinue before IMP administration. Subjects will be summarized separately for each enrollment. The subject ID used for each enrolment will be provided in listings to identify the subject.

Premature discontinuation will be regarded if a patient meets the qualification criteria but leaves the study prior to having completed all scheduled visits.

Completers will be those patients who completed all visits as scheduled.

The following statistical output will be provided:

Table 15.1.1 Analysis Sets – Enrolled Analysis Set

Number and percentage of patients included in the ES, SAF sets will be provided by dose group and overall. Percentages will be based on the number of patients in the ES.

Table 15.1.2 Screening Failures – Enrolled Analysis Set

Number and percentage of the screening failures will be summarized by reasons associated with the discontinuation. Percentages will be based on the number of patients in the ES.

Table 15.1.4 Patient Disposition – Safety Analysis Set

Number and percentage of patients who completed the study as scheduled, who discontinued prematurely including the reason of discontinuation will be summarized by dose group and overall based on the SAF.

Table 15.1.5 Number of Patients by Country and Site – Safety Analysis Set

Number and percentage of patients in each country and site will be presented by each dose group and overall based on the SAF.

Table 15.1.6 Number of Patients by Visit – Safety Analysis Set

Number and percentage of patients attending each scheduled visit will be presented by each dose group and overall based on the SAF.

Figure 15.1.1 Flow Chart of Patient Disposition – Enrolled Analysis Set

The number of patients with the occurrence of each protocol milestone will be displayed. The number of screening failures and discontinuations as well as their reasons will also be summarized.

Listing 16.2.1.1 Patient Disposition – Safety Analysis Set

The overall disposition listing will include study completion status, termination date as well as the primary reason of premature termination.

Listing 16.2.1.2 Screening Failures – Enrolled Analysis Set

Screening failures will be listed based on the ES, including the reason of discontinuation.

Listing 16.2.1.3 Patient Visits – Enrolled Analysis Set

All visit dates will be listed by patient.

5.1.2 Protocol Deviations

Protocol deviations (PDs) are deviations from the procedures outlined in CSP PDs are classified as follows:

- **Important PDs:** A subset of PDs that may significantly impact the completeness, accuracy, and/or reliability of key study data or critical processes or that may significantly affect a subject's rights, safety, or well-being. For example, important PDs may include enrolling subjects in violation of key eligibility criteria or failing to collect data necessary to interpret primary endpoints, as this may compromise the scientific value of the trial.
- **Non-important PDs:** Not meeting the criteria above. Typically, deviations which are not related to collection of primary or key secondary endpoint data or PDs that are not adversely related to subject rights or wellbeing.

The following statistical output will be provided:

Table 15.1.3 Important Protocol Deviations – Safety Analysis Set

The number and percentage of subjects with important protocol deviations, including protocol deviation categories, will be summarized by dose group and overall. Percentages will be based on the number of subjects in the SAF. PDs will be summarized in the overall population as well as within each trial site.

Listing 16.2.1.4 Important Protocol Deviations – Safety Analysis Set

Patients with important protocol deviations will be listed.

5.1.3 Inclusion/Exclusion

The study specific inclusion/ exclusion criteria are presented in Section 8 of the CSP. For each criterion, as appropriate, a response of “Yes/No” is to be obtained at Screening and checked again prior to allocation to treatment, at Visit 2.

The following statistical output will be provided:

Listing 16.2.1.5 Inclusion Criteria Not Met and Exclusion Criteria Met – Enrolled Analysis Set

Inclusion criteria which were not met and exclusion criteria which were met will be listed.

5.2 Demographic and Other Baseline Characteristics

5.2.1 Demographics and Baseline Characteristics

The following demographic and baseline characteristics were collected:

- Age (years)
- Sex at birth
- Childbearing potential status,
- Race,
- Smoking status,
- Height,
- Weight
- Body mass index (BMI)
- HLA typing [REDACTED]
- Immunization against Covid-19 status (yes/no)
- History of confirmed Covid-19 infection status (yes/no) and date
- ECG (result: normal/ abnormal and clinical relevance)
- Infectious Disease Screen (Anti-HIV-1/2, HBs-Ag, Anti-HBc, Anti-HCV, Screening for syphilis)

HLA typing results will not be reported.

The following statistical output will be presented:

Table 15.1.7.1.1 Demographics – Safety Analysis Set

Table 15.1.7.1.2 Demographics – Modified Safety Analysis Set

Demographic data (age, sex at birth and race) will be summarized by each dose group and overall. The modified safety analysis set summary will be performed by treatment cycle subgroup.

Table 15.1.7.2.1 Baseline Characteristics – Safety Analysis Set

Table 15.1.7.2.2 Baseline Characteristics – Modified Safety Analysis Set

Weight, height, BMI data, HLA typing and smoking status will be summarized by each dose group and overall. The modified safety analysis set summary will be performed by treatment cycle subgroup.

Listing 16.2.1.6.1 Demographics and Baseline Characteristics – Enrolled Analysis Set

Demographic and baseline characteristic data will be listed for patients in the ES.

Listing 16.2.1.6.2 Infectious Disease Screen – Enrolled Analysis Set

Infectious disease screen results will be listed

5.2.2 Multiple Sclerosis History

The following information about MS disease history and status at Visit 1 will be presented:

- Time since first MS symptoms (months)
- Time since first MS diagnosis (months)
- Number of relapses in the last 12 months prior to Visit 1
- Number of relapses in the last 24 months prior to Visit 1
- Number of total relapses in the past 10 years (1-3, 4-6, 7-10, >10)

Time since first MS symptoms and diagnosis in months will be calculated as follows:

$$Time\ (month) = \frac{Date\ of\ Visit\ 1 - Date\ of\ first\ MS\ symptoms/ diagnosis + 1}{30.4375}$$

Imputations for incomplete first MS diagnosis or symptoms date:

- 15th of the corresponding month, if the month and year are available but the day is missing.
- the 2nd of July of the corresponding year, if the year is available but the day and month are missing.

Imputed date will be used for calculation of the duration in months. Dates as collected will be included in the listings.

The following statistical output will be presented:

Table 15.1.8 MS History – Safety Analysis Set

MS history parameters as defined above will be presented by dose group and overall based on the SAF.

Listing 16.2.1.7 MS History – Enrolled Analysis Set

MS history data will be listed for patients in the ES.

5.2.3 Medical History

All medical conditions within the last 30 days prior to Visit 1 as well as all relevant conditions of more than 30 days prior to Visit 1 except for diagnosis of MS will be collected in the electronic case report form (eCRF).

Medical history is classified as:

- **Prior medical conditions** are the conditions which started and ended prior to Visit 1.
- **Ongoing medical conditions** are the conditions which are marked as ongoing at Visit 1 or with a stop date at or after Visit 1

If the stop date of a medical history condition is incomplete or missing, it will be assumed to be ongoing except if the incomplete stop date indicates that the condition stopped prior to the Visit 1.

The following statistical output will be provided:

Table 15.1.9.1 Prior Medical Conditions – Safety Analysis Set

Table 15.1.9.2 Ongoing Medical Conditions – Safety Analysis Set

Medical history will be summarized displaying counts and percentages of patients having at least one medical condition and will be presented by SOC and by PT within SOC. SOC and PT within SOC are to be sorted by descending order of overall incidence. Percentages will be based on the number of patients in the SAF.

Listing 16.2.1.8 Medical History – Enrolled Analysis Set

Medical history conditions will be listed for patients in the ES.

5.3 Prior and Concomitant Medications

All concomitant and prior medications including symptomatic therapies for MS administered within 30 days prior to Visit 1 as well as MS disease modifying therapies used within 10 years prior to Visit 1 or during the safety follow-up period will be documented in the eCRF.

Plasmapheresis and non-pharmacological therapies used for medical history or adverse event will be documented as well.

Medications and therapies will be classified as ‘prior’, ‘concomitant’ or ‘post-treatment’ based on start/stop dates:

- **Prior medications/therapies** are defined as those medications/therapies starting and ending prior to Visit 1.
- **Concomitant medications/therapies** are defined as medications/therapies started at or after Visit 1 and include medications/therapies started prior to the Visit 1 but continued after the visit.
- **Post-treatment medications/therapies** are defined as medications/therapies which started during the safety follow-up phase.

If the start or stop date of a medication/therapy is incomplete or missing, it will be assumed to be concomitant except if the incomplete start or stop date indicates that the medication/therapy stopped prior to the Visit 1 or started after the treatment phase.

The following statistical output will be provided:

Table 15.1.10.1 Prior Medications and Therapies – Safety Analysis Set

Table 15.1.10.2 Concomitant Medications and Therapies – Safety Analysis Set

The number and percentage of patients with at least one medication within each ATC 2nd level subgroup and substance name (or combination of substances) will be presented by dose group and overall based on the SAF. The ATC 2nd level subgroups and substance names within ATC 2nd level subgroup will be ordered by descending overall incidence.

Listing 16.2.1.9 Medications and Therapies – Enrolled Analysis Set

All medications, prior, concomitant and post-treatment, will be listed for patients in the ES.

5.4 Exposure to IMP

Patients of all three dose groups will receive treatment with CLS12311 within 13 weeks from enrolment in the study. CLS12311 will be administered at [REDACTED] for sentinel patients and [REDACTED] for all other patients. CLS12311 will be manufactured from blood donations taken at [REDACTED]

The following blood donation and IMP exposure data will be collected in the eCRF:

- Eligibility for blood donation
- Date of blood donation
- Donated blood volume (mL)
- Status of blood production release

- Blood group compatibility
- Date of IMP application
- Application start and end time
- Completion status (complete/incomplete/not done)
- Discomfort following medication infusion
- Date and time of discharge

IMP application will be considered as incomplete if at least one bag is applied incompletely. If the batch number for a bag is collected as “NA”, the infusion completion status will be considered as “Not Done”.

The following statistical output will be provided:

Table 15.1.11 Exposure to IMP– Safety Analysis Set

Number and percentage of patients by number of blood donations, IMP application status by visit as well as number and percentage of patients who completed one IMP cycle and who completed both IMP therapy cycles will be provided by dose group and overall based on the SAF. Number and percentages of patients who received at least one infusion of IMP and who received at least one infusion of IMP in the second treatment cycle will be provided as well.

Listing 16.2.2.1 Blood Donation – Safety Analysis Set

Listing 16.2.2.2 Application of IMP – Safety Analysis Set

Blood donation and IMP application data will be displayed for each patient based on the SAF.

5.5 Safety Analysis

5.5.1 Adverse Events

All medical conditions that started after the informed consent including clinically relevant worsening of previous medical conditions will be documented as adverse events (AEs) in the eCRF. AEs might either be observed by the Investigator during scheduled clinical examinations (e.g. physical examination, AE assessment, see below) or during unscheduled clinical examinations or reported by the patient.

Adverse event data includes:

- adverse event term
- start/stop dates or ongoing
- intensity (Grade 1 - mild, Grade 2 - moderate, Grade 3 - severe, Grade 4 - life-threatening, Grade 5 - death)
- relationship to study treatment (related, not related)
- relationship to blood donation (related, not related)
- action taken with study treatment (dose not fully applied, dose delayed, dose not applied, treatment permanently discontinued, patient other – specified)
- other actions (blood donation delayed, blood donation with reduced volume, no further blood donations, patient withdrawn from the trial, other – specified)
- outcome of event (recovered/resolved, recovering/resolving, not recovered/not resolved, recovered/resolved with sequelae, fatal, unknown)
- seriousness (yes/no)
- AE of special interest (AESI)

All AEs will be presented in listings.

Summaries of adverse events will include AEs defined as **treatment-emergent adverse events (TEAEs)**, defined as AEs with the first onset or worsening after the blood donation for CLS12311 production.

If the start date of an AE is incomplete or missing, it will be assumed to be treatment-emergent except if the incomplete start date or the stop date indicates that the event started prior to the blood donation for CLS12311.

Adverse events will also be assigned to study periods (see Section 4.6) based on their onset dates. If the date of an AE is incomplete or missing, it will be assumed to have occurred in each period which could be covered by the incomplete dates.

Adverse events will be further assigned to the following categories:

- **Serious Adverse Events (SAEs):** defined as AEs considered by the investigator as serious, including AEs with a missing seriousness assessment.
- **Related TEAEs:** AEs assessed as “Related” to study treatment or blood donation, including events with missing IP relationship assessment.
- **TEAEs leading to discontinuation:**
 - AEs for which “Action taken with study treatment” is indicated as “Treatment permanently discontinued”
 - AEs for which “Other action taken” is documented as “No further blood donations” or “Patient withdrawn from the trial”
- **TEAEs leading to death:** AEs documented as having a “fatal” outcome.

The intensity or severity of an adverse event is defined according to the Common Terminology Criteria for Adverse Events (CTCAE, version 5.0, 2017) and provided in Table 3.

Table 3 Adverse Event Intensity Classification

Intensity	Explanation
Mild (Grade 1)	
 • Asymptomatic or mild symptoms • Clinical or diagnostic observations only • Intervention not indicated
Moderate (Grade 2)	
 • Moderate, minimal, local or non-invasive intervention indicated limiting age-appropriate instrumental activities of daily living (ADL)
Severe (Grade 3)	
 • Severe or medically significant but not immediately life-threatening; hospitalization or prolongation of hospitalization indicated; disabling symptoms limiting self-care activities of daily living
Life-threatening (Grade 4)	
 • Life-threatening consequences: urgent intervention indicated
Death (Grade 5)	
 • Death related to AE or to multiple sclerosis

AEs of special interest are defined as severe AEs (Grade of ≥ 3) which are related to the IMP and occurring within one day following infusion of CLS12311/placebo: dyspnea, tachycardia, fever, chills, malaise, shock, infection, allergic reaction, renal or liver failure. Adverse events of special interest will be assessed by the investigator.

TEAEs will be summarized using crude and exposure-adjusted incidence rates. A crude incidence rate will be calculated as number of patients with a TEAE divided by number of patients at risk (at the beginning of the study). An exposure-adjusted TEAE incidence rate per 1 patient-year will be defined as number of patients who experienced a TEAE divided by the total time from the blood donation until occurrence of the event for those who experienced an event, or the end of the safety follow-up for those who did not, multiplied by 365.25, among patients at risk at the beginning of the study:

$$I_{AE} = \frac{n}{\sum_i t_i} \times 365.25 = \frac{n}{T} \times 365.25$$

where n is the total number of patients with the corresponding AE, t_i is equal to the study day of the first corresponding AE for each patient or end of the safety follow-up, T is total time from blood donation until the first event or safety follow-up.

The following statistical output will be provided:

Table 15.2.1.1 Overall Summary of TEAEs – Safety Analysis Set

An overview of TEAEs:

- TEAEs
- Non-serious TEAEs
- Serious TEAEs
- TEAEs related to study treatment or blood donation
- Serious TEAEs related to study treatment or blood donation
- \geq Grade 3 TEAEs
- TEAEs leading to discontinuation
- TEAEs related to study treatment or blood donation leading to discontinuation
- TEAEs leading to death
- TEAEs of special interest

will be displayed by the dose group and overall, for the patients in the SAF.

Table 15.2.1.2.1 Incidence of TEAEs – Safety Analysis Set

Table 15.2.1.2.2 Exposure Adjusted Incidence of TEAEs – Safety Analysis Set

Table 15.2.1.3.1 Incidence of Non-Serious TEAEs – Safety Analysis Set

Table 15.2.1.3.2 Exposure Adjusted Incidence of Non-Serious TEAEs – Safety Analysis Set

Table 15.2.1.4.1 Incidence of Serious TEAEs – Safety Analysis Set

Table 15.2.1.4.2 Exposure Adjusted Incidence of Serious TEAEs – Safety Analysis Set

Table 15.2.1.5.1 Incidence of TEAEs Related to Study Treatment or Blood Donation – Safety Analysis Set

Table 15.2.1.5.2 Exposure Adjusted Incidence of TEAEs Related to Study Treatment or Blood Donation – Safety Analysis Set

Table 15.2.1.6.1 Incidence of Serious TEAEs Related to Study Treatment or Blood Donation – Safety Analysis Set

Table 15.2.1.6.2 Exposure Adjusted Incidence of Serious TEAEs Related to Study Treatment or Blood Donation – Safety Analysis Set

Table 15.2.1.7 Incidence of TEAEs Leading to Discontinuation – Safety Analysis Set

Table 15.2.1.8 Incidence of TEAEs Leading to Death – Safety Analysis Set

Table 15.2.1.9 Incidence of Adverse Events of Special Interest – Safety Analysis Set

Crude and exposure-adjusted incidence rates of TEAEs will be summarized by dose group, SOC and PT. SOC and PTs within each SOC will be ordered by descending number of adverse events in the total column. Tables showing crude incidence rates will be summarized by study period and overall.

Table 15.2.1.10.1 Incidence of TEAEs by Intensity – Safety Analysis Set

Table 15.2.1.10.2 Incidence of TEAEs by Intensity – Modified Safety Analysis Set

TEAEs will be summarized as above within each severity category. The modified safety analysis set summary will be performed by treatment cycle subgroup.

All AE data will be listed as follows:

Listing 16.2.3.1 Adverse Events: MedDRA Coding

MedDRA system organ class and preferred terms assigned to each reported AE name will be displayed.

Listing 16.2.3.2 Adverse Events: General – Enrolled Analysis Set

Listing 16.2.3.3 Non-Serious Adverse Events – Safety Analysis Set

Listing 16.2.3.4 Serious Adverse Events – Safety Analysis Set

Listing 16.2.3.5 Adverse Events of Special Interest – Safety Analysis Set

Listing 16.2.3.6 Adverse Events Leading to Discontinuation – Safety Analysis Set

Listing 16.2.3.7 Adverse Events Leading to Death – Safety Analysis Set

All AEs will be displayed by patient including the PT of an AE, start and stop dates, duration and other characteristics of AEs.

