### 5.2.3 Rationale for the Study Design

CLS12311 is given for the first time in humans, hence the clinical trial is designed to assess safety and tolerability of three dose regimens of CLS12311.

The study will provide data on the safety of a single treatment cycle given in an ascending dose of CLS12311 and will further assess the safety and tolerability of a second treatment in a subset of patients.

Initially, the safety and tolerability of a single treatment cycle of CLS12311 will be assessed in three dose groups in a total of 9 patients. Each dose group will start with a sentinel patient, who will inform about the safety of the treatment in the same dose group. To ensure the safety of dosing in the next patient a time frame of at least four days is defined prior to dosing of the next patient. The definition of this time frame is based on preclinical data showing complete processing of peptide-coupled RBCs in the first 24h after infusion (see IB 5.3). Immediate reaction to the therapy, e.g. hyperacute immune activation and cytokine release or thrombotic events, would be expected in the first hours after treatment. Due to the individual manufacturing of each product and related logistics, only one patient will be treated per week. The treatment will start in the lowest dose groups (2 patients). Further dosing in the higher dose groups (mid dose 3 patients, high dose 4 patients) will be initiated only after safety analysis of the respective prior dose group. During the course of the study the safety and tolerability of a second treatment cycle of CLS12311 will be evaluated in 6 of the 9 patients who received a first treatment cycle. The first patient in each dose group (sentinel patient) will not receive a second treatment cycle of CLS12311, only. Further, patients in each dose group will receive a second treatment in [REDACTED] of the

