##### 12.1.1.1 Adverse Events (AEs)

AEs might either be observed by the Investigator during scheduled clinical examinations (e.g. physical examination, AE assessment, see below) or during unscheduled clinical examinations

or reported by the patient. AEs will have to be documented throughout the trial as described in Section 13. Event description, start/stop dates, severity, relationship to treatment (i.e. blood donation, CLS12311 or placebo), outcome and seriousness (yes or no) will be recorded.

Of particular interest are the following classes of AEs:

- Treatment related AEs
- Treatment related SAEs
- AEs of special interest (AESIs) are AEs considered severe and related to the IMP occurring within one day (i.e. occurring on the treatment day or on the day after treatment) following infusion of CLS12311/placebo: dyspnea, tachycardia, fever, chills, malaise, shock, infection, allergic reaction, renal or liver failure.

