### 13.4.5 Risks of Therapy

The tolerance protocol that is proposed here has been extensively used in rodents for many years, with no major safety issues arising. For a complete summary of safety information, refer to the Investigator's Brochure. From the extensive experience with peptide-coupled cells we do not expect any significant hematopoietic or organ toxicity in humans. Data from two phase I trials with myelin peptide-coupled cells in MS patients are consistent with this assumption and did not reveal any signs of toxicity in any of the nineteen patients who have been treated [57]; ETIMSred Trial unpublished).

**Aggregates:** The formation of aggregates is a major concern in cell-based therapies. Aggregates might cause thromboembolic events, particularly in the lungs after intravenous infusion, but also other venous and arterial vascular compartments. The peptide-coupling procedure induces changes in the deformability of RBCs and the surface of the membrane, which might cause thromboembolism. Pre-clinical studies did not reveal any thromboembolic events following single or repeated administrations of peptide-coupled RBCs. In line with preclinical experience two prior studies in MS patients using either PBMCs coupled with seven myelin peptides or RBCs coupled with seven myelin peptides were tolerated well in MS patients. The following measures were taken to reduce the risk of embolism: 1) formation of aggregates will be carefully checked and excluded in every product prior to release and infusion, and 2) peptide-coupled RBCs as well as uncoupled RBCs will pass through a 40 µm filter in a standard blood transfusion kit. Appropriate monitoring of patients during and after infusion is mandatory to ensure appropriate medical care.

**Hypersensitivity and cytokine response:** In pre-clinical experiments and two phase I trials (Lutterotti et al., 2013; ETIMSred Trial unpublished) the i.v. use of peptide-coupled cells did not show any risk of anaphylaxis. Cytokine response to the drug product has not been observed in animals, and our in vitro data in human cells did not reveal any cytokine response. Patients will be monitored to provide immediate adequate medical measures in case anaphylaxis should occur (see section 14.5). In case of severe allergic (anaphylactic) reactions, standardized medical treatment should be applied. An example for an emergency treatment is given in the Appendix 24.2.

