##### **19.1.3 Data Safety Monitoring Board (DSMB)**

A Data and Safety Monitoring Board (DSMB) consisting of at least 3 independent MS- and trial experts will be chartered to review the safety of the trial. Beside tolerability and safety of CLS12311, the DSMB will also evaluate signs of worsening of MS assessed by new lesions on brain MRI and occurrence of relapses and disability progression based on EDSS.

After both patients in the low dose group and all three patients in the medium dose group have completed [REDACTED], the Sponsor's medical expert(s) will decide based on (S)AEs and relapses, whether the next dose level of the treatment can be applied.

As soon the last patient in the high dose group has completed [REDACTED] safety data (including MRI data, relapses and EDSS) of all patients will be evaluated by the DSMB. Finally, after the last patient in the high dose group has completed [REDACTED] the DSMB will meet again to evaluate safety of the 12-week follow-up after the second treatment cycle in all patients.

The DSMB shall give recommendations on the following main outcomes:

- stop further treatment or lower further dosing of individual patients
- stop recruitment and/or treatment or lower dose for a specific dose group
- stop recruitment and/or treatment for the clinical trial
- continue the clinical trial as per protocol
- any other trial modification (e.g. additional visits, assessments)

Any recommendation will be explicitly documented in the meeting minutes.

Based on the DSMB recommendations, the Study Steering Committee, consisting of the Sponsor and selected country Investigators, will decide on actions to be taken as outlined above.

For the DSMB meetings, the DSMB will receive patient listings and statistical summaries, consisting of at least the following in addition to all available data on the patient(s) that made the meeting necessary:

- All patients who experienced SAEs (including relationship and severity)
- All patients who experienced AEs (including relationship and severity)
- All patients who experienced AEs within one day following infusion of CLS12311/placebo including severity and relationship
- All patients who experienced a relapse
- Number of new brain lesions (CEL and new/enlarging T2)
- EDSS scores
- Safety relevant protocol deviations

Detailed requirements on the presentation of listings and summaries, as well as details of the premise and the scope of the DSMB, will be specified in the DSMB Charter.

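### No planned adverse-event table isolates infusion reactions of every grade: the only infusion-timed AE outputs are the AESI ones, limited to Grade 3 or higher, IMP-related events from a fixed list with no thrombotic or embolic term

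*SAP*

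**What the plan says.** SAP 5.5.1 states that "AEs of special interest are defined as severe AEs (Grade of ≥ 3) which are related to the IMP and occurring within one day", counted from a CLS12311 or placebo infusion. The definition comes from Protocol 12.1.1.1, which sets the window as "occurring on the treatment day or on the day after treatment" and gives the terms as "dyspnea, tachycardia, fever, chills, malaise, shock, infection, allergic reaction, renal or liver failure". The list is closed. It feeds Table 15.2.1.9 and one row of the overview in Table 15.2.1.1.

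The remaining AE tables run on a different clock. SAP 4.5 makes the first blood donation Day 1. SAP 4.6 starts each treatment cycle at a donation. SAP 5.5.1 defines treatment-emergent from the donation and splits the crude incidence tables by study period. It also defines related events as related to study treatment or to blood donation, although the eCRF records the two relationships separately.

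On acute risk, Protocol 5.2.3 says: "Immediate reaction to the therapy, e.g. hyperacute immune activation and cytokine release or thrombotic events, would be expected in the first hours after treatment". Protocol 13.4.5 says "The formation of aggregates is a major concern in cell-based therapies" and then names the harm: "Aggregates might cause thromboembolic events, particularly in the lungs after intravenous infusion".

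For the DSMB, Protocol 19.1.3 requires a broader item: "All patients who experienced AEs within one day following infusion of CLS12311/placebo including severity and relationship".

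**The concern.** The primary objective is safety and tolerability, and the product is an infusion whose acute effects the protocol expects within hours. A reader of the final tables will want to know how often patients reacted around an infusion, how severely, and whether this rose with dose. As planned, only severe, related, listed events are summarised against infusion time.

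A dose-related rise in mild or moderate chills or dyspnoea on infusion days would be spread through tables that also hold donation reactions and some 48 weeks of unrelated events. Protocol 13.4.1 gives donation its own acute reactions, such as vasovagal syncope and, rarely, hypotension. A donation reaction and an infusion reaction with the same preferred term and grade, in the same cycle, would fall in the same cell, including in the related-event tables. The synopsis treats moderate related events as important enough to trigger a DSMB meeting (three patients at one dose level), yet such events cannot enter the infusion-timed AE table at all.

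**Working it through.** The plan states no figure on this point, and SAP 2.6 says that no formal sample size calculation was done. The check is a reading of every AE output in SAP 5.5.1 and 9.1, followed by a count of days.

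**1. What each output can show**

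| Output | Clock | Grade | Causality | Terms |
|---|---|---|---|---|
| 15.2.1.9; AESI row of 15.2.1.1 | within one day of infusion | 3 or higher | IMP-related | ten listed |
| 15.2.1.2 to 15.2.1.4 (all, non-serious, serious) | from donation; crude tables by study period | any | any | any |
| 15.2.1.5, 15.2.1.6 (related) | from donation; crude tables by study period | any | study treatment or donation, pooled | any |
| 15.2.1.7, 15.2.1.8 (discontinuation, death) | from donation; by study period | any | any | any |
| 15.2.1.10.1 and .2 (by intensity) | from donation; by study period | each grade | any | any |
| 15.2.9 (vital signs, not AEs) | before, during and up to 2 h after infusion | not applicable | not applicable | temperature, heart rate, blood pressure |

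No AE row combines infusion timing with all grades, and none separates IMP-related from donation-related events across all grades.

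**2. Could a thromboembolic event enter through a listed symptom?** Not reliably. Protocol 13.2.1 says that once a clear diagnosis is made, its signs and symptoms are generally not recorded separately, with exceptions for atypical or extreme manifestations and an option for serious events. A diagnosed embolism would usually be coded as the diagnosis, which is not on the list.

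**3. How small is the infusion window?** Inputs: 9 patients, of whom 3 are sentinels with one cycle and 6 have two cycles (SAP 2.3.1); two treatment days per cycle (Protocol 5.2.2); a window of the infusion day plus the next day (Protocol 12.1.1.1); at least 48 weeks per patient, including a 17-week treatment phase (Protocol 15.1). Windows are taken not to overlap.

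- Infusion days: 3 × 2 + 6 × 4 = 30.
- Window patient-days: 30 × 2 = 60.
- Planned follow-up: 9 × 48 × 7 = 3,024 patient-days.
- Share: 60 / 3,024 = 2.0%.
- Per patient: 4 days (one cycle) or 8 days (two cycles). That is 4/336 = 1.2% to 8/336 = 2.4% of follow-up, or 4/119 = 3.4% to 8/119 = 6.7% of the treatment phase.

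Splitting by study period therefore still leaves the window a small part of each count.

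**4. Infusion days with CLS12311.** In the low-dose group the second treatment day of each cycle is placebo only (Protocol 10.2.1). CLS12311 days are low 3, medium 10 and high 14, in total 27 of 30. The other 3 are placebo-only days, which a table by infusion would show apart.

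**The case against.** The strongest reply is that little is lost. Grade 1 and 2 events appear by dose group and study period in Table 15.2.1.2.1, by grade in Tables 15.2.1.10.1 and 15.2.1.10.2, and individually in Listing 16.2.3.2. A thrombotic event would appear in the same outputs, and in the serious tables if serious. With nine patients, AE dates can be read against the infusion dates in Listing 16.2.2.2. Table 15.2.9 gives temperature, heart rate and blood pressure around each infusion by dose group. Because Protocol 13.1.1 keeps many vital-sign abnormalities out of AE reporting, that table may show changes that no AE table would. The eCRF also records discomfort after infusion. The SAP follows the protocol's AESI definition, and Protocol 16.1.2 promises no infusion-timed AE table. All of this stands. It makes the point a matter of presentation, but it leaves infusion tolerability by dose to be rebuilt by hand from listings. The listing shells are in a separate appendix not available here, so time since infusion may already be shown there.

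Four stronger readings are tempting and not supported:

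- **That milder or thrombotic events are hidden.** They are reported, but not against infusion time.
- **That the protocol calls thromboembolism a major concern.** In 13.4.5 that phrase describes aggregate formation; thromboembolism is the possible consequence, and the same paragraph reports none in pre-clinical studies.
- **That a probably empty AESI table measures the defect.** At an assumed 1% risk of a qualifying event per infusion day, and assuming independence, the chance of no event is 0.99^30 = 74% (0.995^30 = 86% at 0.5%; 0.98^30 = 55% at 2%). These figures reflect the small trial and the assumed rates, not the filters.
- **That the AESI list must be changed.** AESI status is assessed by the investigator and collected in the eCRF. Widening it after data review would mean reassessing events, and the added table makes this unnecessary.

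**Conclusion.** The point holds as a gap in the planned summaries. The AESI outputs are the only AE summaries tied to infusion, and they exclude Grade 1 and 2 events, events judged unrelated to the IMP, and any thrombotic or embolic diagnosis. No other AE table separates the infusion window, about 2.0% of planned patient-days, from the rest, and the related-event tables do not separate infusion from donation. The 2.0% rests on full planned dosing, the minimum 48 weeks for all nine patients, and non-overlapping windows; no event rate is assumed.

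An empty Table 15.2.1.9 should not be read as showing good infusion tolerability. With no event among all nine patients, the exact one-sided 95% upper bound on the true proportion is 1 − 0.05^(1/9) = 28.3%; among the four high-dose patients it is 1 − 0.05^(1/4) = 52.7%. That weakness comes from the sample size and would apply to any zero count.

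This is a worthwhile, low-cost addition. It is neither an error in the existing tables nor a departure from the protocol.

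**What to change.** Add one table to SAP 5.5.1 and 9.1: all TEAEs with onset on the infusion day or the next day, any grade and any causality, by dose group, treatment cycle and infusion. Show maximum grade, give IMP-related separately from donation-related, and group thrombotic and embolic terms. Add a derived variable, days since last infusion, to Listing 16.2.3.2. Leave the AESI definition, Table 15.2.1.9 and the AESI row of Table 15.2.1.1 unchanged.

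The table mirrors the item that the DSMB already receives, and it uses dates and causality fields already in the eCRF. The cost is one table and one derived variable; if the database is locked, the SAP's own route is an Addendum discussed in the Clinical Study Report. The downside is that some unrelated events will fall in the window, and the causality split lets the reader see them as such.
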